9.1.1. Total disease burden; cumulative lifetime incidence

A cross-sectional design (incidence) will be used to assess the total disease burden of AA, stratified by sociodemographic groups.

9.1.2. Disparities in the impact of AA on mental health, work impact and healthcare utilisation

A matched-cohort design will be used for incidence of AA related: Mental health conditions; work impact; healthcare utilisation.

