8. RESEARCH QUESTION AND OBJECTIVES

8.1. Study Objectives

The overall purpose of the study is to provide an estimate of the cumulative lifetime incidence of AA in the population overall and by sociodemographic groups (sex, ethnicity, deprivation, geographic location and urban-rural status). Moreover, to perform a subgroup analysis in the AA population to identify health-related disparities across people in different socioeconomic strata, geographical distribution, sex and ethnic groups. The disparities that will be considered are AA associated: Mental health conditions; healthcare utilisation; and work impact (time off work and unemployment).

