9. RESEARCH METHODS

9.1. Study design

The study will use retrospectively collected anonymised data from all eligible patients in the Oxford-Royal College of General Practitioners (RCGP) Research and Surveillance Centre (RSC) dataset at the date of data extraction. The cohort to be used for this study has already been specified for previous work as follows:

All adults and adolescents (aged 12+) registered with practices contributing data to RCGP RCS between January 1, 2009 and December 31, 2018, will be eligible for inclusion in the study. People who have opted out of record sharing will not be included (approximately 1.8% of the adult population) and have not been uploaded to the RCGP RCS database. Cumulative lifetime incidence of AA will be estimated using cases of incident AA occurring during the observational study period (January 1, 2009 and December 31, 2018). For all analyses, the overall results including both adults

(aged 18+) and children (aged 12-17) will be published, with stratification by sex, ethnicity, deprivation quintile, geographic region and urban/rural classification.

The assessment of any associations with baseline characteristics and the outcomes of interest (objectives 2-4) will be assessed using Cox proportional hazards models (time to event outcomes) and Poisson regression (repeated event outcomes) models. Three different adjustment sets will be used for each endpoint analysis. These include: an unadjusted model, a sex and age adjusted model, and a multivariable model with an adjustment set of: body mass index (BMI), smoking status, alcohol use, and common comorbidities: type 2 diabetes, hypertension, atrial fibrillation, angina, acute myocardial infarction, stroke, heart failure, chronic liver disease, dementia, rheumatoid arthritis, asthma, chronic obstructive pulmonary disease, chronic kidney disease, malignancy and inflammatory bowel disease.

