9.2.3. Inclusion criteria

Patients must meet all of the following inclusion criteria to be eligible for inclusion in the study:

1. The cohort for this study will consist of all adults and children (aged 12+) contributing to RCGP RCS database during the study period (between January 1, 2009 and December 31, 2018 inclusive).
2. The AA population consists of patients newly diagnosed with AA at any point during the study period.

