9.3. Variables

The variables to be utilised are listed below:

Variable	Role	Operational definition
Age	Baseline characteristic, subgroup variable, and potential confounder	Age will be defined as of the index date.
Sex	Baseline characteristic, subgroup variable, and potential confounder	Identified from primary care records using clinical codes.
Socioeconomic deprivation	Baseline characteristic, subgroup variable and potential confounder	Defined using the Index of Multiple Deprivation which is divided into national quintiles.
Ethnicity	Baseline characteristic, subgroup variable, and potential confounder	Identified from primary care records using clinical codes.
UK geographic region	Baseline characteristic, subgroup variable, and potential confounder	The United Kingdom will be divided into nine regions: Greater London, South East, South West, West Midlands, North West, North East, Yorkshire and the Humber, East Midlands, and East of England. Geographic region will be captured from enrollment data.
Urban/Rural classification	Baseline characteristic, subgroup variable, and potential confounder	Defined as urban or rural area which will be captured from enrollment data.
Alopecia Areata	Case definition	Identified from primary care records using clinical codes.
Depressive episodes	Outcome	Defined by the International Statistical Classification of Diseases and Related Health Problems 10th Revision (ICD10) classification, and identified using algorithms validated or use in UK primary care data.
Recurrent major depression	Outcome	Defined by the International Statistical Classification of Diseases and Related Health Problems 10th Revision (ICD10) classification, and identified using algorithms validated or use in UK primary care data.
Anxiety disorders	Outcome	Defined by the International Statistical Classification of Diseases and Related Health Problems 10th Revision (ICD10) classification, and identified using algorithms validated or use in UK primary care data.
Dermatology referrals	Outcome	Identified from primary care records using clinical codes.
Primary care visits	Outcome	Identified from primary care records using clinical codes.
Referrals for psychological therapy	Outcome	Identified from primary care records using clinical codes.
Psychiatric reviews	Outcome	Identified from primary care records using clinical codes.

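### The AA versus comparator models for Objectives 2 to 4 omit ethnicity, deprivation, region and urban/rural class, and no stated matching rule covers these factors

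*Combined protocol and SAP*

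**What the plan says.** Section 9.1.2 gives the design for mental health, work impact and healthcare utilisation in one sentence: "A matched-cohort design will be used for incidence of AA related: Mental health conditions; work impact; healthcare utilisation". No section names a matching variable, a matching ratio or an index date for comparators, and the table in Section 9.3 gives no variable a matching role.

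Section 9.1 sets three adjustment sets for every endpoint: "These include: an unadjusted model, a sex and age adjusted model, and a multivariable model with an adjustment set of: body mass index (BMI), smoking". The third set goes on to drinking and a list of comorbidities. The section also says that all analyses will be reported "with stratification by sex, ethnicity, deprivation quintile, geographic region and urban/rural classification". It does not say whether a comparator is placed in a stratum by their own group or by that of the matched AA patient.

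In Section 9.3 the role of age, sex, ethnicity, region and urban/rural class is "Baseline characteristic, subgroup variable, and potential confounder", and deprivation has the same role. Section 7 reports that AA is more common at lower socioeconomic status and in Black, Asian and mixed ethnic groups, with peak incidence at age 25-29.

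Section 9.7.1 bases its power statement on people with and without AA, so non-AA comparators are intended.

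**The concern.** A covariate that the plan itself calls a potential confounder should be handled by matching, by the model or by restriction. For ethnicity, deprivation, region and urban/rural class, the protocol commits to neither matching nor adjustment. Stratified reporting deals with one factor at a time and leaves the others free to differ between the AA and comparator arms within each stratum.

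This matters because the study is about disparities. If AA patients come more often from groups with a higher (or lower) background rate of recorded depression, consultations or sick notes, part of that difference will be read as an effect of AA. If the imbalance varies between strata, it will be read as a difference in AA's impact between groups, which is the question behind two of the three primary objectives.

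**Working it through.** **1. The plan's own figure, as a yardstick.** Inputs from Section 9.7.1: 80% power, 5% significance, background 10% (depression) and 15% (anxiety), n = 6007 with AA. Stated detectable differences: 1.2 and 1.5 points. The number of comparators per AA patient, r, is not stated, and two-sided testing is assumed. The Kelsey formula is

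n(AA) = (1.960 + 0.842)² × p̄(1 − p̄) × (r + 1) / (r × d²), with p̄ = (p₁ + r·p₀)/(1 + r).

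Solving for d at n = 6007:

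| r | depression (points) | anxiety (points) |
|---|---|---|
| 1 | 1.59 | 1.87 |
| 2 | 1.35 | 1.60 |
| 3 | 1.27 | 1.51 |
| 4 | 1.23 | 1.45 |
| 5 | 1.20 | 1.42 |
| 10 | 1.14 | 1.36 |

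Of these ratios only 1:4 rounds to both stated values. The match is by rounding only: at exactly 1.2 points and r = 4, p̄ = (0.112 + 4 × 0.10)/5 = 0.1024, and n = 7.849 × 0.1024 × 0.8976 × 1.25 / 0.012² ≈ 6263, which is 4% above 6007. The figures therefore imply several comparators per AA patient but cannot be reproduced uniquely. They use one background risk per condition for everyone, and they address the overall AA contrast only, not differences between groups.

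**2. Which confounders are covered.** Setting Sections 9.1, 9.1.2 and 9.3 side by side:

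| Factor | Confounder in 9.3 | Unadjusted | Age-sex | Multivariable, as listed | Matched on |
|---|---|---|---|---|---|
| Age, sex | yes | no | yes | not listed | not stated |
| Ethnicity, deprivation, region, urban/rural | yes | no | no | no | not stated |
| BMI, smoking, alcohol, comorbidities | yes | no | no | yes | not stated |

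The middle row is covered nowhere. Age and sex are covered in one model only, unless the multivariable set is meant to build on the age-sex set, which the text does not say.

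**3. Where bias can enter.**
- *Overall contrast.* AA frequency differs by ethnicity and socioeconomic status (Section 7). Comparators chosen without regard to these factors will have a different mix.
- *Within one stratum.* With comparators placed by their own ethnicity, ethnicity cannot confound inside an ethnic stratum. Deprivation, region and urban/rural class still can. Placing comparators this way also breaks the matched sets unless ethnicity was a matching factor, so balance on age and sex is no longer secured. The age-sex model restores it; the multivariable model as listed does not.

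**4. How large.** The documents give no group-specific risks, so the values below are assumptions. Take one two-level factor with background risks p_low and p_high, and let a and c be the shares of AA patients and comparators in the higher-risk level. With no AA effect at all,

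apparent risk difference = (a − c) × (p_high − p_low).

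The imbalance needed for a spurious 1.2 points is a − c = 1.2 / (p_high − p_low):

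| p_low, p_high (assumed) | gap (points) | a − c needed |
|---|---|---|
| 10%, 12% | 2 | 1.2/2 = 60 percentage points |
| 10%, 14% | 4 | 1.2/4 = 30 |
| 8%, 14% | 6 | 1.2/6 = 20 |
| 6%, 14% | 8 | 1.2/8 = 15 |

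A single factor therefore needs a sizeable imbalance to create the whole detectable difference. Smaller imbalances shift the estimate in proportion, and several factors can add up.

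**The case against.** Four replies deserve weight.

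- *The rule may be written elsewhere.* Section 9.9 defers detailed methods to a SAP, and Section 9.1 says the cohort was specified for earlier work. That is fair: the finding concerns the text available. But Section 9.1 restates the earlier cohort without a matching rule, Annex 1 lists no stand-alone documents, and Section 7 says the earlier study was not designed to assess the socioeconomic gradient as a primary outcome. The three adjustment sets are stated here, and they omit the four factors.
- *Disparities may be meant within AA patients only.* Section 8.1 proposes "to perform a subgroup analysis in the AA population to identify health-related disparities". In that reading comparator mix does not arise. Section 9.1.2 and the power statement point the other way, and the protocol should say which contrast is meant. A within-AA comparison of ethnic groups would still lack adjustment for deprivation, region and urban/rural class.
- *The multivariable set may be cumulative.* If so, the age and sex point falls; the other four factors remain uncovered.
- *Deprivation is measured at data extraction* (Section 9.2.2), after the index date. Adjusting for it is imperfect. The plan already stratifies on the same measure, so this is a caveat rather than a reason to leave it out.

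Two stronger readings are tempting, and the documents do not support them.

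First, a reader might infer that comparators cannot enter the study, since "Patients must meet all of the following inclusion criteria to be eligible for inclusion in the study" and criterion 2 is "The AA population consists of patients newly diagnosed with AA at any point during the study period". But criterion 1 reads "The cohort for this study will consist of all adults and children (aged 12+) contributing to RCGP RCS database during the study period", criterion 2 is worded as a definition, and Sections 9.1, 9.1.2 and 9.7.1 presuppose people without AA. This is loose drafting.

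Second, a reader might infer that each group's AA effect is measured against other groups' background risk. With an assumed true ratio of 1.30, own-group risk 13%, other groups 10% and 20% of comparators from the same group, that would give 1.30 × 0.13 / (0.2 × 0.13 + 0.8 × 0.10) = 1.59. It requires comparators to inherit the AA patient's group label. No section says so, and stratified reporting more naturally places each person in their own group.

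**Conclusion.** The concern holds as a specification gap with a possible, unquantified bias. Four factors that the plan labels potential confounders are in no adjustment set and under no stated matching rule. Age and sex are missing from the multivariable set as listed. Following the stated models can therefore leave AA versus comparator estimates confounded, overall and within a stratum.

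The direction and size cannot be derived from the documents. The 15 to 60 point range is only a calibration: it rests on assumed risks, one two-level factor and no AA effect. The bias disappears if the matching already covers these factors and the analysis preserves the matched sets. The finding does not show that any estimate is wrong, and it does not show that comparators are excluded.

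**What to change.** - In Section 9.1, add age, sex, ethnicity, deprivation quintile, region and urban/rural class to the multivariable AA versus comparator model.
- Estimate disparities with AA-by-group interaction terms together with group main effects, or draw comparators from the same group. Exact matching on all six factors is not needed.
- In Section 9.1.2, state the matching variables, the ratio and the comparator index date, and say that each comparator is placed in a stratum by their own characteristics.
- Section 9.11 expects substantial missing ethnicity. Keep a not-recorded category or impute, and name the sensitivity analysis.
- As a drafting correction only, word criterion 2 of Section 9.2.3 so that it applies to the AA arm.

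The cost is small, because the variables are already listed in Section 9.3 and the data are already extracted (Section 9.8). With four age bands and five ethnic groups (the list in Section 9.2.2 read as Black, Asian, White, mixed and other), the main effects add 3 + 1 + 4 + 4 + 8 + 1 = 21 parameters, or 22 with a not-recorded ethnicity level. If the plan's 10% depression figure applied over follow-up, the AA arm alone would give about 6007 × 0.10 = 601 events. The model can bear this, at the price of slightly wider intervals in small groups.

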9.2. Setting

The RCGP RSC cohort is drawn from a large GP practices network across England, currently covering a registered population of 2.6 million people, representing a broadly representative sample of the UK.¹⁰

9.2.1. AA Definition

People diagnosed with AA will be identified using diagnosis codes specific to the condition.¹¹ People will be considered to have an AA diagnosis if they had an AA specific diagnosis code and, in the subsequent 365 days, no code for an alternative diagnosis (scarring alopecia¹², traction alopecia, congenital alopecia, androgenetic alopecia, telogen effluvium, tinea capitis, trichotillomania, or secondary syphilis of the scalp).

Incident cases will be defined as people with a first ever diagnosis code of AA during the study period. People with a diagnosis of AA prior to the study period will be excluded. To increase certainty that an AA diagnosis was incident, those diagnosed within six months of registering with a practice will be excluded.

9.2.2. Sociodemographic subgroups

Age, sex, socioeconomic status, ethnicity, major regions of England and urban/rural classification will comprise the sociodemographic factors used for stratification of the outcome measures.

Ethnicity will be grouped using the standardised definitions of major UK ethnic groups: Black, Asian, White mixed, and others.¹³

Socioeconomic status (SES) will be defined using the national deprivation measure; index of multiple deprivation (IMD) and stratified into quintiles of deprivation according to the national distribution.¹⁴ IMD is calculated at the point of data extraction, using patient postcode.

Age will be stratified into four age categories: children aged 12-17, 18-29, 30-49 and 50+ based on our previous research into incidence of AA.²

Geographical distribution will consist of two subgroups including; geographic region and urban/rural classification. Geographic region within England comprises; Greater London, South East, South West, West Midlands, North West, North East, Yorkshire and the Humber, East Midlands, and East of England.

9.2.3. Inclusion criteria

Patients must meet all of the following inclusion criteria to be eligible for inclusion in the study:

1. The cohort for this study will consist of all adults and children (aged 12+) contributing to RCGP RCS database during the study period (between January 1, 2009 and December 31, 2018 inclusive).
2. The AA population consists of patients newly diagnosed with AA at any point during the study period.

9.2.4. Exclusion criteria

Patients meeting any of the following criteria will not be included in the study:

1. People with the alternative non-AA diagnoses (section 9.2.1).
2. People with AA diagnosis within 6 months of registration.
3. People with less than 1 year of follow up within the dataset.
4. People over the age of 95.

9.3. Variables

The variables to be utilised are listed below:

Variable	Role	Operational definition
Age	Baseline characteristic, subgroup variable, and potential confounder	Age will be defined as of the index date.
Sex	Baseline characteristic, subgroup variable, and potential confounder	Identified from primary care records using clinical codes.
Socioeconomic deprivation	Baseline characteristic, subgroup variable and potential confounder	Defined using the Index of Multiple Deprivation which is divided into national quintiles.
Ethnicity	Baseline characteristic, subgroup variable, and potential confounder	Identified from primary care records using clinical codes.
UK geographic region	Baseline characteristic, subgroup variable, and potential confounder	The United Kingdom will be divided into nine regions: Greater London, South East, South West, West Midlands, North West, North East, Yorkshire and the Humber, East Midlands, and East of England. Geographic region will be captured from enrollment data.
Urban/Rural classification	Baseline characteristic, subgroup variable, and potential confounder	Defined as urban or rural area which will be captured from enrollment data.
Alopecia Areata	Case definition	Identified from primary care records using clinical codes.
Depressive episodes	Outcome	Defined by the International Statistical Classification of Diseases and Related Health Problems 10th Revision (ICD10) classification, and identified using algorithms validated or use in UK primary care data.
Recurrent major depression	Outcome	Defined by the International Statistical Classification of Diseases and Related Health Problems 10th Revision (ICD10) classification, and identified using algorithms validated or use in UK primary care data.
Anxiety disorders	Outcome	Defined by the International Statistical Classification of Diseases and Related Health Problems 10th Revision (ICD10) classification, and identified using algorithms validated or use in UK primary care data.
Dermatology referrals	Outcome	Identified from primary care records using clinical codes.
Primary care visits	Outcome	Identified from primary care records using clinical codes.
Referrals for psychological therapy	Outcome	Identified from primary care records using clinical codes.
Psychiatric reviews	Outcome	Identified from primary care records using clinical codes.
Time off work for illness	Outcome	Defined using primary care codes for 'sick leave' or the issuing of a Med 3 certificate indicating time off work for illness
Unemployment	Outcome	Defined using primary care codes indicating unemployment or incapacity from work (IB113 [incapacity benefit] form or ESA113 form [Employment Support Allowance, which replaced IB113 from January 2011])
Body mass index	Potential confounder	Identified from primary care records using clinical codes.

Smoking status	Potential confounder	Identified from primary care records using clinical codes.
Alcohol use	Potential confounder	Identified from primary care records using clinical codes.
Type 2 diabetes	Potential confounder	Identified from primary care records using clinical codes.
Hypertension	Potential confounder	Identified from primary care records using clinical codes.
Atrial fibrillation	Potential confounder	Identified from primary care records using clinical codes.
Angina	Potential confounder	Identified from primary care records using clinical codes.
Acute myocardial infarction	Potential confounder	Identified from primary care records using clinical codes.
Stroke	Potential confounder	Identified from primary care records using clinical codes.
Heart failure	Potential confounder	Identified from primary care records using clinical codes.
Chronic liver disease	Potential confounder	Identified from primary care records using clinical codes.
Dementia	Potential confounder	Identified from primary care records using clinical codes.
Rheumatoid arthritis	Potential confounder	Identified from primary care records using clinical codes.
Asthma	Potential confounder	Identified from primary care records using clinical codes.
Chronic obstructive pulmonary disease	Potential confounder	Identified from primary care records using clinical codes.
Chronic kidney disease	Potential confounder	Identified from primary care records using clinical codes.
Malignancy	Potential confounder	Identified from primary care records using clinical codes.
Inflammatory bowel disease	Potential confounder	Identified from primary care records using clinical codes.

9.4. Primary Endpoints

Objective 1: An incident diagnosis of AA is the date of the first diagnosis code in the record and no alternative diagnosis that merits exclusion (any form of scarring alopecia¹², traction alopecia, congenital alopecia, androgenetic alopecia, telogen effluvium, tinea capitis, trichotillomania, or secondary syphilis of the scalp) diagnosed in the subsequent 365 days from date of AA diagnosis.

Objective 2: Mental health condition outcomes will be assessed up to two years post-AA diagnosis and will comprise new onset depressive episodes, recurrent major depression, and anxiety disorders, defined by the International Statistical Classification of Diseases and Related Health Problems 10th Revision (ICD10) classification, and identified using algorithms validated for use in UK primary care data.

Objective 3: Healthcare utilisation outcomes will comprise primary care visits, dermatology referrals, referrals for psychological therapy (including those via IAPT; Improving Access to Psychological Therapies) and psychiatric reviews in the two years post AA diagnosis.

